1.2 Secondary Objectives

- 1.2.1** To record preliminary evidence of efficacy of PD-0332991 in children with recurrent CNS tumors
- 1.2.2** To evaluate CDK4/6, cyclin D1-3, Ink4a-ARF copy-number variations in available tumor tissue by array comparative, genomic hybridization (aCGH)
- 1.2.3** To explore the potential relationships between the pharmacokinetics of PD-0332991 and pharmacodynamic response (e.g. percentage change in absolute neutrophil count (ANC), platelet counts)
- 1.2.4** To explore the pharmacogenetic polymorphisms in PD-0332991 metabolizing enzymes and transporters and relate these polymorphisms to PD-0332991 pharmacokinetics

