2.4.2 Rationale for Pharmacokinetic Studies

Because the pharmacokinetics of this agent are relatively unknown in the pediatric population, this information will be essential for evaluating toxicity and disease response and for refining dosing in future clinical trials of PD-0332991. The results of these studies will provide the basis for assessing the relationship between the disposition of PD-0332991 in adult and children. Mandatory pharmacokinetic studies are needed to characterize the disposition of PD-0332991 in this patient population. Insights into the biologically active dosage will be gained by relating PD-0332991 systemic exposure (e.g., AUC) to results of pharmacodynamic studies (e.g., percentage change in ANC and platelets compared to baseline).

In vitro studies indicate that PD-0332991 is a substrate of CYP3A4, and dexamethasone is a known inducer of CYP3A4. Thus, one might expect lower exposures of PD-0332991 when administered concurrently with dexamethasone. Indeed, following multiples doses of PD-0332991 in A5481004 Phase 2 (dosing Schedule B), the mean PD-0332991 24-hr trough drug concentrations seem to decrease with time. The mean PD-0332991 trough concentrations on Cycle 1 Day 8, Cycle 1 Day 11, and Cycle 2 Day 11 were 45.33, 44.09, and 32.00 ng/mL, respectively, which is suggestive of a decreased PD-0332991 exposure when administered after dexamethasone-mediated enzyme induction has occurred. It should be noted that the exposure of PD-0332991 observed in this study is considerably lower compared to those observed in Studies A5481001 and A5481003 at the dose levels likely due to the induction effect of dexamethasone. Hence, patients who are receiving dexamethasone will have optional plasma PK studies done following discontinuation of this drug.

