5.2.1 The following are Dose-Limiting Toxicities (DLT's)

- A PD-0332991 (IBRANCE) related adverse event will be considered dose-limiting if it leads to a dose reduction or permanent cessation of treatment during the first course of therapy. All dose modifications in all courses are to follow the guidelines provided in section 6.2.

- Inability to receive the next cycle of PD-0332991 (IBRANCE) within two weeks of the last dose because of lack of hematologic recovery or persisting non-hematologic toxicity.

5.2.1.1 Non-hematologic dose limiting toxicity is defined as:

- Any grade 4 non-hematologic toxicity
- Any grade 3 non-hematologic toxicity with the exception of:
 - Grade 3 nausea and vomiting of < 5 days
 - Grade 3 diarrhea and/or electrolyte disturbances which have not been maximally treated
 - Grade 3 AST/ALT elevation that returns to levels meeting eligibility criteria within 7 days of study drug interruption and does not recur upon restarting drug.
- Any Grade 2 non-hematologic toxicity that persists for > 7 days and is considered medically significant or sufficiently intolerable by patients requires treatment interruption.

5.2.1.2 Hematologic dose limiting toxicity is defined as:

- Grade 3 neutropenia with fever and sepsis
- Any Grade 4 hematologic toxicity with the exception of lymphopenia
- Grade 3 thrombocytopenia and/or requiring a platelet transfusion on 2 separate days within a 7-day period

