6.2 Hematologic and Non-Hematologic Adverse Events and Management

Table 8

Event	AE Grade or Observation	Dose Modification
Diarrhea or other non-hematologic toxicity	Grade 1 or 2	Maintain dose; continue anti-diarrheal treatment.
	Grade 3 (non-dose limiting)	Hold PD-0332991 (IBRANCE) and maximally treat. If toxicity resolves to meet on study parameters within 14 days of drug discontinuation or (as outlined in Section 5.2.1.1), restart treatment at the same dose.
	Grade 3 or 4 (dose limiting)	Hold PD-0332991 (IBRANCE) and maximally treat. If toxicity resolves to meet on study parameters with 14 days of drug discontinuation, restart treatment at next lower dose level if patient at dose level 2 or 3 and meets BSA requirements for the next lower dose level. If patient at dose level 1 or with BSAs smaller than what is required should come off treatment permanently. If toxicity does not resolve to meet study eligibility parameters within 14 days of drug discontinuation, the patient must be removed from protocol therapy. If dose limiting toxicity recurs in a patient who has resumed treatment at the reduced dose level, the patient must be removed from protocol therapy.
Hematologic	Grade 1 or 2	Maintain dose.
	Grade 3 (non-dose limiting)	Maintain dose.
	Grade 3 or 4 (dose limiting)	Hold PD-0332991 (IBRANCE). Counts should be checked at least twice weekly (3-4 days apart) during this time. If toxicity resolves to meet on study parameters with 14 days of drug discontinuation, restart treatment at next lower dose level, if patient is at dose level 2 or 3 and meets BSA requirements for the next lower dose level. If patient at dose level 1 or with BSAs smaller than what is required should come off treatment permanently. If toxicity does not resolve to meet study eligibility parameters within 14 days of drug discontinuation, the patient must be removed from protocol therapy. If dose limiting toxicity recurs in a patient who has resumed treatment at the reduced dose level, the patient must be removed from protocol therapy.

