9.2.2.1 Sampling Strategy

On Day 1 of Course 1, serial blood samples for PD-0332991 (IBRANCE) pharmacokinetic studies will be collected at the following times: pre-dose and at 0.5, 1, 2, 4, 8 (± 1), 10 (± 0.5) [optional], 24 (± 4), and 48 (± 4) hours after the oral dose. **In order to obtain the 24 and 48-hour time points, the dose on Day 2 will be held. It is crucial that the 48-hour time point be obtained prior to dose administration on Day 3.**

On Day 21 of Course 1, serial blood samples for PD-0332991 (IBRANCE) pharmacokinetic studies will be collected at the following times: pre-dose and at 1, 2, 4, 8 (± 1), 10 (± 0.5) [optional], and 24 (± 4) hours after the dose (prior to the next administered dose).

For children less than 13 kg, contact [name] or his designee [REDACTED] for a sampling strategy with reduced blood requirements.

Pharmacokinetic Studies after Discontinuation of Dexamethasone (if consented)

Any patient who received dexamethasone during the mandatory PD-0332991 (IBRANCE) pharmacokinetic studies should have serial blood samples obtained at least 14 days after discontinuation of dexamethasone, and after 14 days of continuous dosing with PD-0332991 (IBRANCE). At a routine clinic visit samples for pharmacokinetic studies should be obtained at the following times: pre-dose and at hours 1, 2, 4, 8 (± 1), 10 (± 0.5) [optional], and 24 (± 4) hours after the dose (prior to the next administered dose).

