Hispanic or Latino	5	+	6	= 11
Not Hispanic or Latino	22	+	22	= 44
Ethnic Category: Total of all subjects	27	+	28	= 55
Racial Category				
American Indian or Alaskan Native	0	+	0	= 0
Asian	3	+	3	= 6
Black or African American	6	+	7	= 13
Native Hawaiian or other Pacific Islander	0	+	0	= 0
White	18	+	18	= 36
Racial Category: Total of all subjects	27	+	28	= 55

13.4 Analysis of the Adverse Event Data:

All patients who receive at least 1 dose of protocol therapy will be included in the safety analyses. Adverse event data will be summarized in stratum specific tables which will incorporate dose, attribution as well as grade information.

13.5 Data analysis plan for the secondary objectives:

Any objective responses (PR+CR) which may be observed in this trial will be described by dose and by histology. We will also report prolonged disease stabilizations in a descriptive fashion.

The biology and PD/PG studies are optional in this trial and thus data will be available only from a subset of patients who are likely to represent a variety of histologies. The data generated as part of these correlative studies will be described and summarized in an exploratory fashion via summary statistics and frequency tables as appropriate.

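### Does calling PD optional in section 13.5, and leaving the AUC for objective 1.2.3 unnamed, put the exposure-count analysis at risk?

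*Combined protocol and SAP*

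**What the plan says.** Objective 1.2.3 is "To explore the potential relationships between the pharmacokinetics of PD-0332991 and pharmacodynamic response", with percentage change in ANC and in platelets as the examples. Section 2.4.2 repeats this, speaking of "relating PD-0332991 systemic exposure (e.g., AUC) to results of pharmacodynamic studies (e.g., percentage change in ANC and platelets compared to baseline", and says of the pediatric PK data that "this information will be essential for evaluating toxicity and disease response and for refining dosing in future clinical trials of PD-0332991". Section 13.5 groups PD with pharmacogenetics and biology: "The biology and PD/PG studies are optional in this trial and thus data will be available only from a subset of patients". For all of these it plans exploratory summary statistics and frequency tables.

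PK is sampled twice in course 1. The Day 1 profile runs to 48 hours, with the Day 2 dose held for it. Section 9.2.2.1 then states: "On Day 21 of Course 1, serial blood samples for PD-0332991 (IBRANCE) pharmacokinetic studies will be collected at the following times", ending at 24 hours. Sections 9.2.2.6 and 13.6 add a population model with individual Bayesian (post hoc) estimates.

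Section 5.2.1.2 lists "Any Grade 4 hematologic toxicity with the exception of lymphopenia" as dose limiting. Table 8 in section 6.2 then holds the drug. On recovery it says to "restart treatment at next lower dose level, if patient is at dose level 2 or 3", given sufficient BSA. Otherwise: "If patient at dose level 1 or with BSAs smaller than what is required should come off treatment permanently".

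**The concern.** Two things look wrong. First, 13.5 appears to give objective 1.2.3 the wrong analysis population, a consenting subset instead of all treated patients.

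Second, several exposure measures are available (Day 1 AUC, Day 21 AUC, a model-based estimate), none is chosen, and the choice is not neutral. A Grade 4 fall found before Day 21 triggers a hold, then a lower dose or the end of treatment. The Day 21 exposure is then missing or reduced because of the response it is meant to explain. Relating Day 21 AUC to the counts would leave out the patients with early deep falls, or give them too low an exposure, and so tend to understate the link between exposure and myelosuppression. Myelosuppression is the main dose-limiting toxicity, and 2.4.2 looks to this relationship for insight into the biologically active dosage.

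**Working it through.** The plan states no sample size, power or error rate for objective 1.2.3, so there is no figure of its own to reproduce.

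**1. Is PD optional?**

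- The table opening section 9 marks as optional pharmacogenetics, PK after dexamethasone, the cyclin/CDK/Ink4a-ARF assay, central pathology review and repository samples. It lists no PD study.
- The calendar (section 10) schedules CBCs before therapy and weekly in course 1, with no consent condition.
- Section 9.2.2 and the calendar require plasma PK in all patients.

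The data for 1.2.3 are therefore collected in every patient whatever 13.5 calls them.

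**2. How far could Day 21 exposure fall?**

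Capsule doses from Appendix D, compared at each BSA where a reduction is possible:

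- 95 to 75 mg/m²: lowest ratio 100/150 = 67% (BSA 1.45), highest 200/225 = 89% (BSA 2.50).
- 75 to 50 mg/m²: lowest 100/175 = 57% (BSA 2.17), highest 100/125 = 80% (BSA 1.83).
- Treatment ends for BSA 0.70–0.92 at level 3, BSA 0.93–1.19 at level 2, and everyone at level 1.

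Assume one compartment, immediate absorption and the adult half-life of 26.5 h (section 2.2.3.3). The share of drug left after 24 h is q = exp(−24 × ln 2 / 26.5) = 0.534. Day 21 AUC(0–24), relative to uninterrupted dosing, is about

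f(1 − q^m) + q^j

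where f is the dose ratio, m the number of doses from restart to Day 21 inclusive, and j the days from the last dose before the hold to Day 21.

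| Last dose before hold | Restart | f | Calculation | Relative AUC |
|---|---|---|---|---|
| Day 8 | Day 16 | 0.889 | 0.889 × (1 − 0.023) + 0.000 | 0.87 |
| Day 15 | Day 20 | 0.667 | 0.667 × (1 − 0.285) + 0.023 | 0.50 |
| Day 15 | Day 21 | 0.571 | 0.571 × (1 − 0.534) + 0.023 | 0.29 |

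If the drug is still held on Day 21 there is no post-dose profile. The mechanism is real.

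**3. Which exposure measures does it reach?**

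- Day 1 AUC: not affected, because it precedes any hold.
- Individual population-model estimate: largely protected if the model is fitted to the doses actually taken. Section 9.2.2.2 records exact sampling and dosing times, and the Appendix E diary records daily date, time and capsule counts.
- Day 21 AUC used alone: affected. No section proposes this analysis.

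**4. How many patients?**

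Section 5.1.2 reports DLTs in 0 of 3, 0 of 6 and 2 of 4 evaluable patients at levels 1, 2 and 3: 2/13 = 15%, both Grade 4 neutropenia. Onset days are not given, so 0 to 2 of them lack an intact Day 21 profile. With weekly counts, a fall first seen at about Day 22 leaves Day 21 PK untouched. Both DLTs were at level 3, which section 13.3 says will not be studied in stratum II.

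**5. Size against sampling error**

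Section 13.3 gives 21 + 4 = 25 patients enrolled at version 8.0, and 21 + 18 = 39 if stratum II fills. For an observed rank correlation of 0.50 (assumed), the Fisher z interval is tanh[0.549 ± 1.96 × √(1.125/(n − 3))]:

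- n = 25: SE 0.226, interval 0.11 to 0.76.
- n = 39: SE 0.177, interval 0.20 to 0.71.

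As an illustration, I simulated 25 patients from a bivariate normal with true rank correlation 0.50 and dropped those with the one or two largest falls. The mean estimate moves down by 0.03 or 0.05, against a sampling standard deviation of about 0.16. In 22% to 24% of samples it moves up.

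**The case for a change.** The strongest case for a change is that the plan contradicts itself and the remedy is cheap. Read literally, 13.5 narrows 1.2.3 to a subset. Summary statistics and frequency tables are thin for an objective that asks about a relationship. Section 13.6 never links its individual estimates to the counts. Section 9.2.2.1 sets 14 days of continuous dosing before the optional post-dexamethasone profile but has no matching condition for using the required Day 21 profile. Stratum II is still accruing, and it starts at the level where Table 8 ends treatment after a dose-limiting fall, so affected patients there would have no Day 21 profile. The step from a hold to a lower dose also makes the distortion systematic, and an AUC reduced to 29% of normal is worse than a missing one: if many patients were affected, a correlation could shrink well beyond the figures above.

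The wording point stands, as does the absence of a named AUC and count window. The bias argument stands only on the condition that Day 21 AUC is used alone and without regard to holds. An analyst relating exposure to counts would have the dosing record, an unaffected Day 1 profile and model-based estimates to hand, and would see who had been held or reduced. The 14-day comparison is weak: the post-dexamethasone profile has no fixed day and needs a dosing condition, whereas Day 21 is fixed by the schedule.

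**Conclusion.** No change to the plan follows. The optional label is a clerical slip that removes no required blood count or PK sample. The unnamed AUC and count window are missing detail in an exploratory secondary objective with no test or decision attached. No stated rule produces a wrong result, and the material for a sensible choice is already planned and collected.

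The known exposure to the problem is 0 to 2 of 13 evaluable stratum I dose-finding patients, and the illustrated shift of 0.03 to 0.05 is well inside sampling error. Dose escalation and the MTD are untouched, and the hold and dosing rules are not in question.

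This rests on three assumptions: that the population model is fitted to the actual dosing record; that few patients have a Grade 4 fall found before Day 21 (onset days, and any such falls in the expansion cohort or stratum II, are not reported); and that adult half-life is a fair guide for the AUC arithmetic. If analysts instead reported Day 21 AUC alone and ignored holds, the concern would apply to that report.

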13.6 Statistical Analysis of Pharmacokinetics

Plasma drug concentrations and pharmacokinetic parameters will be presented in tabular and graphical form. Pharmacokinetic parameters of interest, such as apparent volume of the central compartment (V_c/F), elimination rate constant (K_e), half-life ($t_{1/2}$), apparent oral clearance (CL/F), and area under the plasma concentration time curve (AUC) will be estimated using compartmental methods. Dose proportionality in pharmacokinetic parameters will be investigated by performing one-way analysis of variance (ANOVA) on dose-normalized parameters.

In addition to estimating individual pharmacokinetic parameters, we will also estimate the population parameters using nonlinear mixed effects modeling methods (NONMEM). This method estimates the population parameters and both the inter- and intra-subject variability. Once the population parameters and corresponding covariance matrix are estimated, individual estimates can be obtained using post hoc analysis.

Because this is a Phase I study, most patients will be treated at very low doses of the agent and will have various diseases; thus, observations of objective responses are expected to be rare. In this setting, correlations of copy number variations of various cell cycle proteins and clinical outcome will be reported descriptively.

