5.1 Agent Administration

PD-0332991 (IBRANCE) is currently available as 75, 100, and 125 mg capsules (No liquid formulation is currently available). PD-0332991 (IBRANCE) will be given oral daily for 21 days followed by a week rest (one course = 28 days) for 24 months (26 courses). The starting dose will be 50 mg/m²/day for stratum I. The starting dose for stratum II will be one dose level below the MTD for stratum I (50 mg/m²/day).

Dosing is based on BSA calculated at the beginning of each course of therapy. The dose prescribed should be rounded to the nearest deliverable dose based on the BSA adjustment and the available capsule sizes. Dosing Tables are available in [Appendix D](#). Patients will be provided with a Medication Diary for PD-0332991 (IBRANCE), instructed in its use, and asked to bring the diary as well as the remaining capsule bottles with them to each appointment. The Patient Diary is available on the PBTC-042 webpage.

PD-0332991 (IBRANCE) should be taken with food. Patients are encouraged to take their dose at approximately the same time each day. Capsules should be swallowed whole (do not chew, crush or open them prior to swallowing). Capsules should not be ingested if they are broken, cracked, or otherwise not intact. Patients should be advised to drink plenty of water or take hydration fluids to avoid dehydration if diarrhea occurs. Patients who vomit a dose of PD-0332991 (IBRANCE) can be re-dosed if capsule is intact in the vomitus, and appropriate anti-emetic therapy should be implemented prior to the next scheduled dose (see [Appendix B](#) for contraindicated anti-emetic medications).

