9.2.2 Plasma Pharmacokinetics Studies

Plasma pharmacokinetic studies will be obtained from all patients enrolled on this study on days 1, 2, 3, 21 and 22 of Course 1 to evaluate the pharmacokinetics of PD-0332991 (IBRANCE). ***On Day 2 of Course 1, the dose of PD-0332991 (IBRANCE) will be held to obtain pharmacokinetic studies.*** No other doses should be held for pharmacokinetic purposes. Serial pharmacokinetic studies will be repeated approximately 2 weeks after discontinuation of dexamethasone in patients who were previously receiving this medication.

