9.2.2.6 Description of Pharmacokinetic analysis

The PD-0332991 plasma concentration-time data will be analyzed with both compartmental and non-compartmental approaches. The noncompartmental analysis will provide an estimate of the maximum concentration (C_{max}), minimum concentration (C_{min}), area under the concentration-time curve, and apparent oral clearance.

Pharmacokinetic data will also be analyzed using nonlinear mixed effects modeling (NONMEM v.7). For PD-0332991, an appropriate compartmental pharmacokinetic model will be fit to the data. Estimated pharmacokinetic parameters may include the absorption rate constant (k_a), apparent oral clearance (CL/F), apparent volume of distribution (V_1/F), peripheral volume of distribution (V_2/F), and distributional clearance (Q/F). The typical population value and inter-individual variability of each parameter will be determined using NONMEM. Demographic and clinical chemistry covariates will be examined graphically (via individual Bayesian parameter estimates) and by using generalized additive modeling. Potentially significant covariates will be tested in the NONMEM population model.

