Appendix D Dosing Tables for PD-0332991 (palbociclib; IBRANCE)

Dose Level 50 mg/m ² /day	Total Daily Dose (mg)	BSA Range		Capsules Required		
		low	high	75 mg	100 mg	125 mg
	75	1.20	1.75	1	0	0
	100	1.76	2.25	0	1	0
	125	2.26	2.50	0	0	1

Dose Level 75 mg/m ² /day	Total Daily Dose (mg)	BSA Range		Capsules Required		
		low	high	75 mg	100 mg	125 mg
	75	0.93	1.16	1	0	0
	100	1.17	1.50	0	1	0
	125	1.51	1.83	0	0	1
	150	1.84	2.16	2	0	0
	175	2.17	2.49	1	1	0
	200	2.50	2.50	0	2	0

Dose Level 95 mg/m ² /day	Total Daily Dose (mg)	BSA Range		Capsules Required		
		low	high	75 mg	100 mg	125 mg
	75	0.70	0.92	1	0	0
	100	0.93	1.16	0	1	0
	125	1.17	1.44	0	0	1
	150	1.45	1.71	2	0	0
	175	1.72	1.97	1	1	0
	200	1.98	2.23	0	2	0
	225	2.24	2.50	0	1	1

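### Section 13.6 tests dose proportionality by one-way ANOVA alone; a power-model slope with a 90% interval would use the same data better (minor, cheap improvement)

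*Combined protocol and SAP*

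**What the plan says.** Section 13.6 gives one sentence on the subject: "Dose proportionality in pharmacokinetic parameters will be investigated by performing one-way analysis of variance (ANOVA) on dose-normalized parameters". It names no scale, slope, interval, alpha or margin, and does not say whether the dose used for normalization is assigned or delivered. It also promises tables and graphs of concentrations and parameters, and a NONMEM population analysis.

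Other relevant text:

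- **Covariates, 9.2.2.6.** "Demographic and clinical chemistry covariates will be examined graphically" and by generalized additive modeling; then "Potentially significant covariates will be tested in the NONMEM population model". Dexamethasone is not named here or in 13.6.
- **Who is sampled, 9.2.2.** "Plasma pharmacokinetic studies will be obtained from all patients enrolled on this study", on days that give a Day 1 and a Day 21 profile in Course 1.
- **Dose, 5.1.** "The dose prescribed should be rounded to the nearest deliverable dose based on the BSA adjustment and the available capsule sizes". Appendix D gives the bands. Minimum BSA is 1.20, 0.93 and 0.70 m² at levels 1, 2 and 3 (3.1.7).
- **Dexamethasone.** Section 2.4.2 expects it to lower exposure through enzyme induction, and 3.2.5.5 allows it on a stable or decreasing dose. Section 5.4.1 has corticosteroid use recorded. Under 9.2.2.1, consenting patients who took it during the mandatory sampling "should have serial blood samples obtained at least 14 days after discontinuation of dexamethasone".

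**The concern.** A one-way ANOVA asks whether any group mean differs. Dose proportionality is a question about a trend: does exposure rise in step with dose? Treating three ordered doses as unordered groups spends a degree of freedom on departures of no particular interest. It also yields a p-value rather than an estimate. With groups of 3, 12 and 6 the likely outcome is a non-significant result, and nothing planned in 13.6 would quantify how large a departure remains compatible with the data.

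Plasma pharmacokinetics is a primary objective (1.1.2), and 2.4.2 makes it the basis for comparing disposition in adults and children. The proportionality analysis is a small part of that.

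**Working it through.** The plan gives no power, alpha or margin for this analysis, so there is no figure to reproduce.

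**Inputs.** Doses are 50, 75 and 95 mg/m². Stratum I sizes are 3/12/6 (Schema), assuming every enrolled patient yields a profile. The CVs are assumptions borrowed from section 2.2.3.3: 24% (Table 6, isethionate capsule), 38% (Table 6, large-particle capsule) and 59% (Table 5, 13 adults). The Table 6 data are from fasted volunteers. None comes from fed children, and that section says food makes exposure more uniform. Also assumed are log-normal exposure, two-sided alpha 0.05 and a true slope b of 1.5. That slope makes dose-normalized exposure 1.9^0.5 = 1.38 times higher at 95 than at 50.

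**Power.** σ² = ln(1 + CV²). The mean log dose is 4.327, so Sxx = 3(0.415²) + 12(0.010²) + 6(0.227²) ≈ 0.827. Both tests have noncentrality λ = (b − 1)²·Sxx/σ². The ANOVA uses F on 2 and 18 df; the slope test uses F on 1 and 19 df. The 90% half-width is t(0.95, 19)·σ/√Sxx = 1.729·σ/0.909.

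| CV | σ | λ | Log-scale ANOVA | Slope test | 90% half-width |
|---|---|---|---|---|---|
| 24% | 0.237 | 3.69 | 33% | 45% | 0.45 |
| 38% | 0.367 | 1.53 | 16% | 22% | 0.70 |
| 59% | 0.547 | 0.69 | 10% | 12% | 1.04 |

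At b = 1.25 both tests are close to the null rate: 11%, 8% and 6% for the ANOVA against 15%, 9% and 7%.

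**If strata are pooled.** At CV 38% and b = 1.5, ANOVA against slope test is:

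- 7/12/6 (enrollment at version 8.0): 25% against 34%.
- 9/24/6 (planned maximum, Stratum II expansion at level 2): 31% against 41%.
- 15/18/6 (planned maximum, expansion at level 1): 40% against 51%.

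**Delivered dose.** Appendix D milligrams divided by the BSA limits give 42.9–62.5, 64.7–85.5 and 81.5–107.5 mg/m². Levels 2 and 3 overlap only at 81.5–85.5. In simulation at 3/12/6 (b = 1.5, BSA uniform from each level's minimum to 2.50), the log ANOVA rejects 26%, 13% and 9% with assigned dose and 31%, 14% and 9% with delivered dose. The slope test gives 46%, 23% and 13% on delivered dose against 45%, 22% and 12% on nominal dose.

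**Body size.** If CL/F did not vary with BSA, AUC would follow total mg = (mg/m²) × BSA, and the slope would shift by the regression of log(BSA) on log(dose). With BSA uniform up to 2.50, the geometric means by level are 1.81, 1.65 and 1.51, with logs 0.594, 0.502 and 0.412. The shift is [3(−0.415)(0.594) + 12(−0.010)(0.502) + 6(0.227)(0.412)]/0.827 ≈ −0.29. With an upper limit of 2.00 it is about −0.32. The ANOVA on dose-normalized values carries the same bias.

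**Dexamethasone (illustrative).** User shares and effect size are not in the documents. The troughs in 2.4.2 fall from 45.33 to 32.00 ng/mL, or 29%, but this is an uncontrolled time trend in another study. If the share of users rises by 10 points per level, the unadjusted slope shifts by 0.315·ln(ratio). That is −0.11 at an assumed AUC ratio of 0.71 and −0.03 at 0.90. With balanced use the shift is zero.

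**The case against.** The strongest reply is that this is a preference about a secondary analysis. Proportionality is not a listed objective, 13.6 says only that it will be investigated, and adult exposure was dose-proportional over 25–225 mg (2.2.3.3). The primary PK results rest on estimated parameters and the NONMEM model, not on this ANOVA, and the planned tables and graphs will show scatter and group sizes. The power gain is modest and is calculated under a log-linear truth, which favors the slope test. All of this stands, and it keeps the point minor. It does not remove the case for an estimate with an interval, which costs almost nothing.

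A second reply is that a slope on mg/m² without body size could itself mislead. That is correct, but the ANOVA shares the bias and a log(BSA) term removes it. A third is that a yes/no dexamethasone flag on the PK day would misclassify a patient who stopped a few days earlier, since 2.4.2 describes enzyme induction and 9.2.2.1 sets a 14-day washout. That also stands, and the fix uses an exposure window.

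A reader might infer more than the documents support:

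- **That the plan treats non-significance as proof of proportionality.** Section 13.6 makes no such claim.
- **That it normalizes by the wrong dose.** It is silent, and the choice changes little.
- **That dexamethasone is ignored.** The covariate step in 9.2.2.6 could admit it, and 9.2.2 already plans that "Serial pharmacokinetic studies will be repeated approximately 2 weeks after discontinuation of dexamethasone". What is missing is a named term and a stated comparison.

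**Conclusion.** The point holds as a minor, cheap improvement. One-way ANOVA is the only stated method for proportionality, and the slope test has higher power in each of the four size scenarios above. The gain at current Stratum I sizes is 33% to 45%, 16% to 22% and 10% to 12%. These figures rest on a true slope of 1.5, log-normal exposure and CVs from adults.

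The fix would not establish proportionality either. Borrowing the 80–125% limits that the protocol uses for bioequivalence, the matching slope range over a 1.9-fold dose span is 1 ± ln(1.25)/ln(1.9), or 0.65 to 1.35. The 90% half-width exceeds 0.35 at every CV tried. The benefit is that the uncertainty becomes visible.

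It would be wrong to conclude that the MTD or the primary PK estimates are compromised: escalation uses DLTs only, and the population model does not depend on the ANOVA. Bias from dexamethasone requires use that differs by dose level, which the documents do not show.

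**What to change.** In 13.6, replace or supplement the ANOVA with a power model: log(AUC) and log(Cmax) on log(delivered mg/m²), fitted separately for Day 1 and Day 21. Report the slope with a 90% CI, and state that a non-significant test is not evidence of proportionality. Show the slope again with a log(BSA) term.

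As sensitivity fits, add dexamethasone exposure and, if Stratum II is pooled, a stratum term. Stratum II has no level 3 (13.3), so stratum is tied to dose. Define dexamethasone exposure as use within a stated window before the PK day, consistent with the 14-day washout in 9.2.2.1.

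A useful clarification in 9.2.2.6 is to name dexamethasone as a candidate covariate on CL/F, and to say that repeat profiles will be compared within patient with Day 21.

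**Cost.** Wording, minor programming and no new samples. Delivered dose follows from capsules and BSA. Steroid use is already recorded, though the window assumes that dates are captured. Added terms widen the 90% half-width at CV 38%:

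- log(BSA) at 3/12/6, simulated with BSA uniform to 2.50 or 2.00: about 0.70 to 0.72–0.74.
- Dexamethasone at 3/12/6: 0.70 to about 0.71–0.76 in simulation with a yes/no term; a window-based term should cost about the same.
- Stratum, from the same regression formula: 0.53 to 0.69 at 7/12/6, 0.48 to 0.51 at 9/24/6, and 0.41 to 0.51 at 15/18/6. This is why it belongs in a sensitivity fit.
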